3 SCHEDULE OF EVENTS

Table 1: Tests and Evaluation Schedule with Visit Windows										
Parameter	Baseline -180 to 0 days	Baseline -60 to 0 days	Enroll - ment and Treatment (day 0)	As Indicated 2 day +3 /-1 days	1 week +/- 2 days	6 weeks +/- 7 days	3 months +/-14 days	6 months +/- 30 days	12 months +/-30 days	24, 36, 48, 60 months +/-30 days
Consent		X								
Medical Urological Hx		X								
Medication Review		X	X	X	X	X	X	X	X	X
IPSS		X			X	X	X	X	X	X
IIEF and MSHQ-EjD		X				X	X	X	X	
Uroflowmetry		X			X	X	X	X	X	
Post Void Residual		X			X	X	X	X	X	
Physical Exam +DRE		X								
PSA	X						X	X	X	
Urinalysis		X	X	If Indicated	If Indicated	If Indicated	If Indicated	If Indicated	If Indicated	
Urine Culture		X		If Indicated	If Indicated	If Indicated	If Indicated	If Indicated	If Indicated	
Ultrasound	X				If Indicated	In indicated	Optional	Optional	Optional	
Cystoscopy	X									
MRI		If Indicated			If Indicated		If Indicated			
Inclusion/Exclusion			X							
ProstaCare Therapy			X							
Fluoroscopy			If Indicated							
Pain VAS			X							
Voiding Trial			If Indicated	X	If Indicated					
Adverse Events			X	X	X	X	X	X	X	X
Device Deficiencies			X							
Risk Benefit Assessment							X		X	
Additional BPH Treatment Review					X	X	X	X	X	X

1 STUDY OBJECTIVES AND DESIGN

1.1 Study Objectives

a. Primary Objectives

The primary objectives of the study are to:

- Demonstrate that BPH symptoms are improved by 6.5 points or more after use of prostaFix Water Electrolysis System as measured by the IPSS on all subjects at 3 months.
- Demonstrate that the treatment does not cause unacceptable rates of serious adverse events (SAE) associated with use of the device.

b. Secondary Objectives

The secondary objective(s) of the study are:

- To characterize changes in Qmax and PVR, sexual function and quality of life.
- To characterize post-treatment recovery measuring treatment tolerability and medication requirements.
- To measure durability up to 12 months after treatment.
- To characterize prostate size and necrosis via MRI (for the first 10-15 subjects only).
- To characterize all adverse events and technical observations on device performance.

1.2 Study Design

The study design is a prospective, multicenter, multinational, single-arm clinical investigation. A total of up to 50 subjects will be enrolled at 2-5 sites. Subject follow-up visits will be conducted at 2-day (if catheterized post procedure), 1 and 6 weeks, and 3 months to reach the primary endpoint visit analysis. The first few subjects will have fluoroscopic confirmation of electrodes placement before treatment, then fluoroscopy is optional. The first 10-15 subjects will have MRI studies at baseline, and the 1 week and 3-month follow-up visits to assess subject safety and treatment effect, then MRI is optional. Subject discomfort will be assessed throughout the treatment using VAS. Follow-up visits will assess BPH symptoms, uroflowmetry parameters, quality of life and adverse events.

Subjects will continue to attend follow-up visits at 6 months and 12 months after treatment to demonstrate treatment durability. After completion of their 12-month follow-up visit, subjects will have the option to continue study participation into the long-term follow-up phase with a yearly visit up to 5 years post treatment.

2 EFFICACY EVALUATION

2.1 Summary of Planned Analysis

The statistical analysis of efficacy is a within-subject analysis in which the significance of changes from baseline are assessed. No interim analyses are planned.

Initial analysis for the study objective will be performed when all subjects treated have completed their 3-month post-treatment visit and will be repeated at 6- and 12-month post-treatment visits. Analyses for this objective will be performed on an intention-to-treat basis, including all subjects treated under the protocol. Long-term analysis will be performed after completion of the 60-month visit for all remaining subjects.

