Executive Protocol Summary

ProstaCare Water Electrolysis System for the Treatment of Benign Prostatic Hyperplasia

CIP #: PC 1.0, Version: 2.1, Date: January 1, 2018

**Sponsored by: ProstaCare Singapore Pte. Ltd.
[name]**

This document is a confidential communication of **ProstaCare Singapore Pte. Ltd.**
Acceptance of this document constitutes the agreement by the recipient that
no unpublished information contained herein will be published or disclosed
without prior written approval from **ProstaCare Singapore Pte. Ltd.**

PROTOCOL SUMMARY

Study Title and Number	Prostafix Water Electrolysis System for the Treatment of Benign Prostatic Hyperplasia Prostafix Protocol # PC 1.0
Device Name	prostaFix Water Electrolysis System
Intended Use	The prostafix Water Electrolysis System is indicated for the treatment of lower urinary tract symptoms (LUTS) secondary to benign prostatic hyperplasia (BPH) in men > 45 years old with prostate volumes between 25 cm ³ and 55 cm ³ .
Purpose	To evaluate the safety and performance of the prostafix Water Electrolysis System in relieving symptoms of urinary outflow obstruction secondary to Benign Prostatic Hyperplasia (BPH).
Primary Objectives	Effectiveness: To demonstrate that BPH symptoms are improved by 6.5 points or more after use of ProstaFix as measured by the IPSS on all subjects at 3 months. Safety: To demonstrate that the Prostafix treatment does not cause unacceptable rates of serious adverse events (SAE) associated with use of the device.
Secondary Objectives	
 - To characterize changes in BPH symptoms, Qmax and PVR, sexual function, and quality of life (QOL) from baseline. - To characterize post-treatment recovery measuring treatment tolerability and medication requirements. - To measure durability at 6- and 12-months following treatment and up to 60 months after treatment for long-term durability. - To characterize prostate size and necrosis via MRI. - To characterize all adverse events (AEs) and technical observations on device performance.

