2.2 Hypothesis to be tested

The primary efficacy objective is to demonstrate that mean IPSS improvement (Δ IPSS) following treatment with the prostaFix Water Electrolysis System exceeds 6.5 points with 95% confidence.

The null and alternative hypotheses associated with this objective can be written as:

$$H_0: \mu_{\Delta IPSS} \leq 6.5 \text{ points}$$

$$H_A: \mu_{\Delta IPSS} > 6.5 \text{ points}$$

where $\mu_{\Delta IPSS}$ is the true underlying value of mean Δ IPSS following a treatment at the 3-month visit and 6.5 points is an objective performance goal (OPG). The objective is met at a given time point by rejection of the null hypothesis in a one-sided t-test at the 5% significance level.

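### The 60-month durability result would rest on men still attending, with no rule for those who left or were re-treated, so it can be overstated

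*SAP*

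**What the plan says.** - **Objective.** The secondary objectives in the Protocol Summary cover durability at 6 and 12 months and "up to 60 months after treatment for long-term durability". The matching objective in SAP 1.1 stops earlier: "To measure durability up to 12 months after treatment".
- **Follow-up.** SAP 1.2 (and Protocol 1.2) make everything beyond the 12-month visit voluntary: "subjects will have the option to continue study participation into the long-term follow-up phase with a yearly visit up to 5 years post treatment".
- **Analysis to 12 months.** SAP 2.1 defines efficacy as a within-subject change from baseline. It states that "Initial analysis for the study objective will be performed when all subjects treated have completed their 3-month post-treatment visit", with repeats at 6 and 12 months, and adds: "Analyses for this objective will be performed on an intention-to-treat basis, including all subjects treated under the protocol".
- **Analysis at 60 months.** One sentence in SAP 2.1: "Long-term analysis will be performed after completion of the 60-month visit for all remaining subjects".
- **Test.** SAP 2.2 sets the hypothesis at the 3-month visit and requires "rejection of the null hypothesis in a one-sided t-test at the 5% significance level".
- **Data collected.** In Protocol section 3, Table 1, both IPSS and the row "Additional BPH Treatment Review" are marked in the column for 24, 36, 48 and 60 months.

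The text available gives no rule for missing visits, for men who do not continue, or for IPSS after another BPH treatment. Part of the SAP was not available, so this absence applies only to what could be read.

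**The concern.** Long-term durability is a protocol objective, and the quantity of interest is how treated men fare at five years. A change from baseline at 60 months can be calculated only for a man who has a 60-month IPSS. Men may decline to continue after month 12, and the plan neither brings the others back into the estimate nor shows how they differed. If men whose symptoms return are more likely to leave, the mean among attenders will be better than the mean among treated men.

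Re-treated men raise a second issue. A man who has further BPH treatment and keeps attending still has IPSS recorded. With no rule for those values, improvement due to the second treatment could be counted as lasting benefit of this device.

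The study has one arm, so no control group would reveal either effect.

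**Working it through.** **1. The plan's own figure.** SAP 2.2 and 2.3 give a goal of 6.5 points, an expected mean change of 10, SD 6, one-sided 5% level and 90% power. The difference is 10 − 6.5 = 3.5. Noncentral-t power is 0.894 at n = 26 and 0.904 at n = 27, so 27 is the minimum; 27 / 0.9 = 30. Both stated sizes reproduce. They concern the 3-month test. No retention, power or precision is stated for 60 months, and the 10% attrition has no stated time horizon.

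**2. Two readings of the long-term sentence.**
- *Analysis set:* the analysis covers men still in follow-up, so leavers are out by definition.
- *Timing:* the analysis is run once the remaining men have had the visit. The set is then undefined, and a man without a 60-month IPSS still has no change score.

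Both readings lead to a mean over attenders.

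**3. Effect of leaving.** Let r be the share remaining, S the mean improvement in those remaining, and L the mean improvement in those who left.

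All-treated mean = r·S + (1 − r)·L

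Overstatement = S − [r·S + (1 − r)·L] = (1 − r)(S − L)

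The documents give neither r nor L, so the values below are assumptions.

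| Share remaining | S − L | Overstatement |
|---|---|---|
| any | 0 | 0 |
| 0.8 | 2 | 0.2 × 2 = 0.4 |
| 0.6 | 4 | 0.4 × 4 = 1.6 |
| 0.5 | 6 | 0.5 × 6 = 3.0 |

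If leavers did better than stayers, S − L is negative and the result is understated.

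A second set of assumptions fixes S = 10:

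| Share remaining | L = 10 | L = 6.5 | L = 0 |
|---|---|---|---|
| 0.9 | 0 | 0.35 | 1.0 |
| 0.7 | 0 | 1.05 | 3.0 |
| 0.5 | 0 | 1.75 | 5.0 |

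In the bottom right cell the all-treated mean is 0.5 × 10 + 0.5 × 0 = 5.0, while attenders show 10.

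**4. Check by simulation.** Here SD 6 is borrowed from SAP 2.3, and the men ranked worst on a score correlated with the 60-month change are the ones who leave. The mean among stayers is inflated as follows, in IPSS points.

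| Share remaining | Correlation 0 | 0.3 | 0.5 |
|---|---|---|---|
| 0.9 | 0 | 0.4 | 0.6 |
| 0.7 | 0 | 0.9 | 1.5 |
| 0.5 | 0 | 1.4 | 2.4 |

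**5. Effect of re-treatment.** If a share q of attenders has been re-treated, their observed mean improvement is M, and a stated rule would assign them V, then using the observed values raises the attenders' mean by q(M − V). The documents give no value for q or M and no rule that fixes V.

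**The case against.** The strongest reply is that the sentence only sets timing. It follows the form of the 3-month rule, which says when that analysis is run. This is a natural reading, and a reader who infers that the SAP expressly restricts the analysis to completers goes beyond the text. It does not close the gap, because step 2 reaches the same mean under either reading.

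Three other inferences are tempting and not supported:

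- *That failed or re-treated men are dropped.* Nothing removes them. A re-treated man who attends is a remaining subject, and the schedule records further treatment to 60 months. His problem is the missing rule for his later IPSS.
- *That the sentence contradicts intention-to-treat.* The intention-to-treat sentence refers to the objective analysed at 3, 6 and 12 months. The 60-month set is unspecified, which is different from contradictory.
- *That durability is overstated.* No passage says who leaves. Satisfied men may also decline yearly visits, in which case the bias could be nil or reversed.

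It is also fair to say that durability is a secondary objective to be measured. The 3.5-point difference belongs to the 3-month sample-size calculation and is not a yardstick for 60 months.

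These points limit the claim to a risk of uncertain size. They do not supply a method for including all treated men, or any display that would show whether leaving was related to outcome.

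**Conclusion.** The point holds as a gap in a secondary analysis that should be closed. As written, the 60-month durability result would describe men still attending, and IPSS after re-treatment could be credited to the device. The first effect is zero if leavers do as well as stayers, and 0.4 to 3.0 points if 50–80% remain and stayers do better by 2 to 6 points. Those ranges are assumptions. The second effect cannot be sized from the documents.

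A reader might infer that the trial's main conclusion is at risk. It is not: the 3-month primary test and the 27 and 30 subjects are untouched.

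Separately, the protocol and SAP disagree on how far the durability objective extends (60 against 12 months).

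**What to change.** Keep the long-term sentence in SAP 2.1 as the timing rule only, and add that long-term analyses include all treated subjects. Then specify:

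1. **Re-treatment.** Report the cumulative incidence of additional BPH treatment from day 0 with all treated men at risk, by Kaplan-Meier or with death as a competing event. State that censoring at non-continuation may be informative.
2. **IPSS change at 24–60 months.** Use a repeated-measures mixed model with every visit. State beforehand an analysis rule under which IPSS after additional BPH treatment is not credited to the device, for example a composite analysis counting re-treated men as having no improvement. Merely setting those values to missing is not enough, since the model would then predict the men as if never re-treated. Because the model assumes data are missing at random, add a sensitivity analysis in which men who left do worse than predicted under that assumption.
3. **Description.** Show the remaining-subjects mean only as a description, with numbers and reasons for leaving, beside the 3- and 12-month IPSS change of men who stayed and men who left.
4. **Objective.** Align the durability objective in SAP 1.1 with the Protocol Summary.

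The cost is SAP wording and some programming. IPSS and additional treatment are already scheduled to 60 months, so no visit or measurement is added. The durability figure may be less favourable. The rules should be fixed before the 60-month data are seen.

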2.2 Hypothesis to be tested

The primary efficacy objective is to demonstrate that mean IPSS improvement (Δ IPSS) following treatment with the prostaFix Water Electrolysis System exceeds 6.5 points with 95% confidence.

The null and alternative hypotheses associated with this objective can be written as:

$$H_0: \mu_{\Delta IPSS} \leq 6.5 \text{ points}$$

$$H_A: \mu_{\Delta IPSS} > 6.5 \text{ points}$$

where $\mu_{\Delta IPSS}$ is the true underlying value of mean Δ IPSS following a treatment at the 3-month visit and 6.5 points is an objective performance goal (OPG). The objective is met at a given time point by rejection of the null hypothesis in a one-sided t-test at the 5% significance level.

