2.3 Sample Size Justification

The SAS proc power procedure was used to estimate the sample size required to reject the null hypothesis with 90% power at the one-sided 5% significance level in a paired t-test. The specific alternative hypothesis and standard deviation of the change in IPSS used in the calculation was derived from the feasibility study and other studies of devices for BPH. This suggested a mean change in IPSS of 10 points and a standard deviation of 6 points could be expected for this device.

Given these assumptions, a sample size of 27 subjects would provide adequate power to reject the null hypothesis. Allowing for a 10% attrition rate, a total of 30 subjects are required for this study. Actual number of subjects enrolled will range from 40-50.

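### Does the SAP let a 6- or 12-month result meet the primary IPSS objective, so that its error exceeds 5%?

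*SAP*

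**What the plan says.** SAP 1.1 sets the primary efficacy objective as an improvement of at least 6.5 points "as measured by the IPSS on all subjects at 3 months"; the Protocol Summary uses the same time point. SAP 1.2 and Protocol 1.2 both name 3 months as the visit at which the primary endpoint analysis is reached.

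SAP 2.2 writes the null hypothesis for the true mean improvement "following a treatment at the 3-month visit and 6.5 points is an objective performance goal (OPG"). The next sentence is the success rule: "The objective is met at a given time point by rejection of the null hypothesis in a one-sided t-test at the 5% significance level".

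SAP 2.1 says that the initial analysis for the study objective takes place once all treated subjects have completed the 3-month visit, and that it "will be repeated at 6- and 12-month post-treatment visits". It plans no interim analyses.

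The later visits have a stated purpose in SAP 1.2: "Subjects will continue to attend follow-up visits at 6 months and 12 months after treatment to demonstrate treatment durability". SAP 1.1 lists this among the secondary objectives: "To measure durability up to 12 months after treatment".

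**The concern.** The phrase about a given time point does something only if there is more than one time point, and SAP 2.1 supplies three. It ties the repeats to the study objective and does not call them durability or secondary analyses. Someone facing a non-significant 3-month result could therefore point to SAP 2.2 and report the objective as met at 6 or 12 months. No sentence expressly forbids this, and there is no multiplicity rule. The null hypothesis is also written for the 3-month mean only, so a test at 6 or 12 months has no hypothesis of its own on the page.

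The trial has a single arm, and its efficacy conclusion rests on one test against a fixed goal. If later visits could rescue a 3-month miss, the 95% confidence claimed in SAP 2.2 would not hold for the objective as a whole.

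**Working it through.** **1. The plan's own figure.** SAP 2.3 sizes the trial to "reject the null hypothesis with 90% power at the one-sided 5% significance level in a paired t-test", assuming "a mean change in IPSS of 10 points and a standard deviation of 6 points could be expected for this device".

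- Difference from the goal: 10 − 6.5 = 3.5. Standardised: 3.5 / 6 = 0.583.
- At n = 27, the noncentrality is 0.583 × √27 = 3.03 on 26 degrees of freedom. Power is 90.4%. At n = 26 it is 89.4%, so 27 is the smallest sufficient n.
- Attrition: 27 / 0.9 = 30.

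The stated 27 and 30 reproduce as a single one-sided 5% test. At the planned enrolment of 40 to 50, power would be 97.6% to 99.2% if all subjects were evaluable. The calculation neither uses nor needs a second chance at a later visit.

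**2. Error if only 3 months decides.** One one-sided test at 5% gives 5.0%.

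**3. Error if any of the three visits could count.** Take the true mean as exactly 6.5 at 3, 6 and 12 months, with equal correlation ρ between the three test statistics:

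P(any rejection) = 1 − Φ₃(1.645, 1.645, 1.645; ρ)

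With ρ = 0 this is 1 − 0.95³ = 14.3%. The part that arises only after a 3-month non-rejection is P(any) − 5.0%.

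| Assumed ρ | Any of three visits | Only after a 3-month miss |
|---|---|---|
| 0 | 14.3% | 9.3% |
| 0.5 | 11.8% | 6.8% |
| 0.7 | 10.3% | 5.3% |
| 0.8 | 9.3% | 4.3% |
| 0.95 | 7.1% | 2.1% |

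Correlation that decays with the number of visits apart (first-order autoregressive) gives 12.3% at 0.5 and 9.7% at 0.8. Simulated t-tests with 27 to 50 subjects give 11.8% to 12.0% at 0.5 and 9.2% to 9.3% at 0.8. The documents state no correlation, so ρ is an assumption throughout.

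**4. Which reading the text supports.**

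| Item | Time point | Where |
|---|---|---|
| Primary objective | 3 months | SAP 1.1; Protocol Summary |
| Primary endpoint visit | 3 months | SAP 1.2; Protocol 1.2 |
| Mean in the null hypothesis | 3 months | SAP 2.2 |
| Initial analysis | 3 months | SAP 2.1 |
| Durability | 6 and 12 months | SAP 1.1 (secondary), SAP 1.2 |

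The rule requires rejection of the null hypothesis, and the sentence before it defines that hypothesis at 3 months. Taken literally, later data cannot reject it. The wording also attaches each verdict to its own visit; it does not say that rejection at any visit is enough. The calculation in step 3 therefore describes a rule that the plan does not contain.

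**The case for a change.** The strongest case for a change is that the sentence deciding success should allow only one reading. The surrounding sections show intent but do not settle the rule, and a clarifying sentence would cost no subjects and no power at 3 months. The missing hypothesis for the later visits is a gap on either reading.

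Part of this stands. The phrasing is loose, and SAP 2.1 could have labelled the repeats as durability analyses. Saying that the primary objective is judged at 3 months only, and that later tests cannot alter that result, would be a harmless clarification. It would, however, only record what the objective, the hypothesis and the visit designation already say. For the later visits, the obvious completion is the same goal and the same one-sided 5% t-test applied to that visit's mean.

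A stronger edit, making the 6- and 12-month analyses purely descriptive, would remove per-visit tests that the SAP plans. That is a choice about how formally to assess durability, not the correction of an error. The same holds for a fixed testing sequence: the chance of at least one false verdict among three per-visit tests is indeed the 9% to 12% above, but the plan makes no familywise claim across its primary and durability results.

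One limit applies to both sides: the protocol supplied is an executive summary without a statistics section, so the absence of an explicit exclusion can be judged only on this text.

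**Conclusion.** No change follows. Followed as written, the plan has one primary efficacy test, at 3 months, with one-sided error of 5.0%; the sample size of 27 evaluable and 30 in total is consistent with that. The 6- and 12-month tests give separate durability verdicts.

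The 9% to 12% figure is arithmetically right but hypothetical. It needs a rule that any one visit suffices, which neither document states; a true mean of exactly 6.5 points at all three visits; and a between-visit correlation of 0.5 to 0.8, which is assumed. What remains is a loosely worded sentence that a competent analyst would read correctly from the rest of the SAP.

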2.3 Sample Size Justification

The SAS proc power procedure was used to estimate the sample size required to reject the null hypothesis with 90% power at the one-sided 5% significance level in a paired t-test. The specific alternative hypothesis and standard deviation of the change in IPSS used in the calculation was derived from the feasibility study and other studies of devices for BPH. This suggested a mean change in IPSS of 10 points and a standard deviation of 6 points could be expected for this device.

Given these assumptions, a sample size of 27 subjects would provide adequate power to reject the null hypothesis. Allowing for a 10% attrition rate, a total of 30 subjects are required for this study. Actual number of subjects enrolled will range from 40-50.

